2.3 Study Population

The study will consist of approximately120 male and female subjects, 18 to 60 years old (inclusive), who are scheduled to undergo elective bilateral lower third molar extraction. The full list of inclusion and exclusion criteria are mentioned in sections 4.1 and 4.2 of the protocol respectively.

Statistical Analysis Plan Version: 2.0

Effective Date: 08OCT2018

2.4 Study Material and Treatment Regimens

DFN-15 is an oral solution containing 25 mg/mL of celecoxib. Each mL of DFN-15 will contain 25 mg celecoxib. DFN-15 will also contain the inactive ingredients, lauroyl polyoxylglycerides, glyceryl caprylate, caprylic/capric triglyceride, polyoxyl 35 castor oil, polyoxyl 40 hydrogenated castor oil, propyl gallate, menthol, magnasweet, sucralose, acesulfame potassium, peppermint flavor, banana flavor, bubble gum flavor, glycerol, ethanol, and water.

DFN-15 and matching placebo are packaged in amber-colored glass bottles containing 4.8 mL solution per bottle (120 mg) and equipped with child-resistant and tamper-evident caps.

Treatment consists of a single dose of either DFN-15 62.5 mg, DFN-15 125 mg, DFN-15 250 mg or matching placebo of total volume of 10 mL of oral solution.

The 10 mL dose will be prepared by a designated unblinded pharmacist at site, as per the randomization schedule. Designated blinded study staff will dose subjects and administer study assessments. Blinded study staff will remain blinded to the dose administered to each subject throughout the study.

2.5 Randomization

A computer-generated randomization scheme will be prepared prior to study initiation.

Subjects will be randomly assigned to treatment with DFN-15 62.5 mg, DFN-15 125 mg, DFN-15 250 mg, or placebo in a 1:1:1:1 assignment ratio according to the randomization scheme. Randomization will occur after the subject has qualifying baseline pain, other post-operative inclusion criteria are met, and all Pre-Dose Baseline assessments have been performed on Day 1. All study doses administered will be according to the treatment assignment. No stratification will be performed as part of the randomization; however, male and female subjects will be enrolled in an approximate ratio of 1:1. Subjects who discontinue after randomization will not be replaced in this study.

2.6 Sample Size Determination

The sample size of 120 subjects for this study was selected without a formal statistical calculation. However, group sizes of 30-40 per group are typically sufficient to detect a treatment effect over placebo in the dental pain model.

3.0 General Analysis and Reporting Conventions

This section discusses general policies to be employed in the analysis and reporting of the data from the study. Departures from these general policies are provided in the specific detailed sections of this SAP. When this situation occurs, the rules set forth in the specific section take precedence over the general policies.

All continuous study assessments will be summarized by treatment and timepoint (as applicable) using descriptive statistics (n, mean, median, SD, minimum, and maximum). All the categorical study assessments, including responder variables, will be summarized by treatment and timepoint (as applicable) using frequency counts and percentages. Changes from baseline

Effective Date: 08OCT2018 for continuous outcomes will be presented as their corresponding continuous measures for

Statistical Analysis Plan Version: 2.0

post-baseline visits. Shifts from baseline for the ECG outcomes will be presented in shift tables by timepoint and treatment group. All study data will be listed by subject, treatment group, and timepoint (as applicable).

No preliminary rounding will be performed; rounding will only occur after the analysis. To round, consider the digit to the right of the last significant digit: if <5, then round down; if ≥5, then round up. Means and medians will be presented with one more decimal place than the precision of the data. Standard deviations will be presented with two more decimal places than the precision of the data. Percentages will be presented with one decimal place. Minimums and maximums will be presented with the same precision as the original data.

All analyses will be performed using the SAS System® version 9.3 or higher. The domain (Study data tabulation Model [SDTM]) and analysis (Analysis Data Model [ADaM]) data sets will be taken as input to the SAS programs that generate the report-ready tables, figures and listings. The SDTM and ADaM data sets will be provided to the sponsor along with display deliveries. The specifications for the domain data sets and analysis data sets will be provided in a separate document.

For all efficacy analyses, subjects will be analyzed according to their randomized treatment group, regardless of the actual treatment received, unless otherwise indicated. For all safety analyses, subjects will be analyzed by treatment group according to the actual product received during treatment, i.e., "as treated."

The following conventions will be used throughout the study analysis:

- Assessment visit times are defined by time after administration of study drug.
- Time T₀ is the time of first treatment with study drug.
- Baseline value is defined as the last valid measurement prior to first treatment administration (prior to T_0).
- Pain Intensity Difference (PID) and changes from baseline are defined as post-baseline value minus baseline value.
- The date of first treatment with study drug is Day 1.
- Percentage PID and percent change from baseline is computed as: (post-baseline value - baseline value) × 100 / (baseline value).
- Treatment difference is computed as DFN-15 mean minus control mean. (Note: for the SPID statistics, for which the treatment goal is to reduce the score over time. improvement will be represented as a negative number.)
- SPID statistics will be computed using the trapezoid rule for computing area under the curve.
- All statistical tests will be two-tailed and at the α = 0.05 significance level
- Duration of an AE will be computed in days or hours as the stop date/time of the event minus the start date/time plus 1. If reported as ongoing at the time of database lock, the stop date is defined as the date of the last visit or the last date of any AE for the subject in the database, whichever is later. Missing dates will be imputed as described in Section 9.2 Table 2.
- The number of days/hours in the study is computed as:

Date/time of study completion /withdrawal - the date/time of first treatment administration (Day 1) + 1.

Statistical Analysis Plan Version: 2.0

Effective Date: 08OCT2018

If duplicate values are obtained at a given timepoint (e.g., repeated vital sign
measurements), the last value will be used unless it is noted that the measurement was
in error for that value. Values that compromise interpretation will not be used in
summaries (e.g., values that were obtained post-dose will not be summarized as predose values).

4.0 Analysis Populations

4.1 Modified ITT Population

The mITT population includes all subjects who are randomized, receive study medication and have recorded at least one post dosing pain intensity (PI) score. This population will be used to summarize and analyze efficacy outcomes and treatment grouping will be based on randomized treatment.

4.2 Safety Population

The safety population includes all subjects who receive a dose of study medication (DFN-15 or placebo). This population will be used to summarize safety and demographic data, and for these summaries, treatment grouping will be based on treatment actually received.

4.3 Per-Protocol Population

The per-protocol population includes all mITT subjects who complete all pain assessments for at least 8 hours post-dose and have no major protocol deviations that impact subject safety or the interpretation of the primary analysis. Major protocol deviations excluding subjects from the Per Protocol population will be defined prior to unblinding (Section 5.2). This population will be analyzed by randomized treatment, unless otherwise indicated in the Blinded Data Review Meeting (BDRM). In the BDRM, a decision may be made to analyze the PP population as per treatment actually received in study by subjects.

4.4 Pharmacokinetic Population (PK)

The pharmacokinetic (PK) population will be determined by the PK Vendor and documented in a separate PK Analysis Plan.

5.0 Patient Summaries

5.1 Disposition of Subjects

A subject is considered randomized once the subject is assigned a treatment randomization number. If a subject is randomized but does not receive treatment, they will be included in the All Randomized population summaries, but no others.

Investigators are instructed to encourage subjects to attend all visits. If subjects are unable or unwilling to return, the reason for the subject withdrawal will be recorded. Subjects who successfully complete the 8-hour post treatment assessment period will be counted as treatment period completers regardless if they complete the study, by returning for the 7 day end of study visit, or not.

All treated/randomized subjects and the populations for which they qualify will be listed. The

number of subjects who are screened, and who fail screening or withdraw consent prior to randomization will be listed and summarized in total. Subjects who are randomized, subjects who are treated, subjects who complete the treatment period of 8 hours on study medication, subjects who complete follow-up, as well as subjects who withdraw early from the study and the reason for withdrawal will be summarized by treatment group and overall in the subject disposition summary tables, both overall and by center (if applicable). Days/Hours in study will be calculated as date/time of subject's last visit minus date/time of study drug administration plus 1. Subjects that complete any portion of a day will be counted as on study during that day.

5.2 **Major Protocol Deviations**

Protocol deviation information will be captured in the CRF and in site logs by site and CRO personnel. All protocol deviations will be designated by the medical monitor(s) as major or minor prior to unblinding. A major deviation is one that may affect the outcome, analysis or interpretation of the study results. If present, major protocol deviations will be summarized and all protocol deviations will be presented in a by-subject listing.

6.0 **Demographic and Other Baseline Characteristics**

6.1 **Demographics and Baseline Characteristics**

Demographic variables include age, sex, race, and ethnicity. Baseline characteristics will include weight (kg) and BMI (kg/m²) as well as the qualifying (baseline) NPRS and 4-point categorical pain intensity scores. Demographics and baseline characteristics will be presented in a by-subject listing and summarized overall and by treatment group for the Safety population and the mITT population, if they differ.

6.2 **Medical History**

Medical history, as collected at screening, will be coded using the Medical Dictionary for Regulatory Activities (MedDRA) version 21.0 and summarized by system organ class (SOC) and preferred term (PT) in a frequency table based on the safety population. The SOC and PT will each be sorted in descending order by overall frequency. Medical histories will also be presented in a by-subject listing using the coded and verbatim history terms.

AEs that occur prior to treatment or that are related to a medical history event will be captured as medical history prior to database lock.

6.3 **Prior and Concomitant Medication**

Prior medications/therapies are those that stop prior to the start of the study medication administration. Any medication/therapy that stops at or after the date and time of start of treatment or those with missing stop dates are considered concomitant medication/therapy. Surgical medications/Anesthesia used during and immediately after surgery will be listed but will not be summarized.

Prior and concomitant medications are collected at screening, and updated throughout the study as needed. Prior and concomitant medications will be coded using the March 1, 2018 version of the WHODrug. Subjects who take concomitant medications will be presented in a by-subject listing of verbatim and coded terms and summarized by drug class and preferred name, overall and by treatment group, for the safety population.

A by subject listing of all prior and concomitant medications will be presented with Surgical medications/Anesthesia used during surgery identified. Additionally, a summary and by-subject listing of concomitant medications that were prescribed or modified at or after the time of

discharge on study day will also be presented.

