9.2 Adverse Events

Treatment-emergent AEs are defined as AEs that start or worsen in severity after the first exposure to study medication through the Day 7 visit. Verbatim terms used by investigators to identify AEs in the CRFs will be mapped to the appropriate preferred (PT) and system organ class (SOC) using a standardized coding dictionary (MedDRA Version 21.0 or higher). All coding will be reviewed prior to database lock. All recorded AEs will be listed, but only TEAEs will be summarized.

Statistical Analysis Plan Version: 2.0

Effective Date: 08OCT2018

In addition to a listing of all TEAEs, separate listings of subjects with SAEs and listings of subjects with severe, treatment related, and AEs leading to premature discontinuation will be provided.

An overall summary will be prepared giving for each treatment group, all DFN-15 groups combined and overall of both the number of events and the number of subjects with TEAEs, SAEs, TEAEs by severity, TEAEs by relationship to treatment, and TEAEs leading to premature discontinuation.

The incidence of TEAEs will be summarized for each treatment group by SOC and PT within SOC (sorted in descending order by overall frequency). These summaries will be given in separate tables for the following categories of TEAEs:

- All TEAEs
- TEAEs leading to premature discontinuation
- SAEs

Also summarized will be TEAEs by maximum severity and by maximum relatedness to treatment. Adverse events will be deemed treatment related if they were recorded as probably, possibly, or definitely related.

If a given subject experiences a TEAE that maps to the same PT more than once, the subject will be counted once for the PT at its greatest severity (i.e., mild, moderate, or severe) and causality (i.e., attribution to study medication).

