15.0 Appendices

15.1 Tables for Final Study Report

Number	Title	Analysis Population
Study Population		
14.1.1	Summary of Subject Disposition	All Subjects
14.1.2.1	Summary of Demographic and Baseline Characteristics	mITT Population
14.1.2.2	Summary of Demographic and Baseline Characteristics (if applicable)	Safety Population
14.1.3	Summary of Medical History	Safety Population
14.1.4	Summary of Concomitant Medications by Drug Class and Medication	Safety Population
14.1.5	Summary of Concomitant Medications by Drug Class and Medication after Discharge	Safety Population
Efficacy	•	·
14.2.1.1	Primary Endpoint: Analysis of Summed Pain Intensity Difference from T0 to T6 (SPID6)	mITT Population
14.2.1.2	Analysis of Summed Pain Intensity Difference from T0 to T6 (SPID6)	PP ['] Population
14.2.1.3	Analysis of Summed Pain Intensity Difference from T0 to T6 (SPID6) by Gender	mITT Population
14.2.1.4	Analysis of Summed Pain Intensity Difference from T0 to T6 (SPID6) by Qualifying Pain Intensity	mITT Population
14.2.1.5	Analysis of Summed Pain Intensity Difference from T0 to T6 (SPID6) by BMI Category	mITT Population
14.2.1.6	Analysis of Summed Pain Intensity Difference from T0 to Other Timepoints (SPID2, SPID4, SPID8)	mITT Population
14.2.1.7	Analysis of Summed Pain Intensity Difference from T0 to Other Timepoints (SPID2, SPID4, SPID8)	PP Population
14.2.2	Summary of Pain Intensity and Pain Intensity Difference by Timepoint	mITT Population
14.2.3	Summary of Pain Intensity and Pain Intensity Difference by Timepoint	PP Population
14.2.4	Analysis of Proportion of 30% and 50% Responders (NPRS)	mITT Population

Number	Title	Analysis
14.2.5.1	Summary of Pain Relief by Timepoint	Population mITT
14.2.5.2	Summary of Pain Relief by Timepoint	Population PP
14.2.5.3	Analysis of Total Pain Relief (TOTPARx)	Population mITT
14.2.5.4	Analysis of Total Pain Relief (TOTPARx)	Population PP
14.2.6.1	Summary of Peak Pain Relief	Population mITT
14.2.6.2	Summary of Peak Pain Relief	Population PP
14.2.7.1	Analysis of Time to Peak Pain Relief	Population mITT
14.2.7.2	Analysis of Time to Peak Pain Relief	Population PP
14.2.8.1	Proportion of Subjects Satisfied with Treatment	Population mITT
14.2.8.2	Analysis of Subject Treatment Satisfaction	Population mITT
14.2.9	Analysis of Time to Perceptible Pain Relief	Population mITT
14.2.10	Analysis of Time to Meaningful Pain Relief	Population mITT
14.2.11	Analysis of Time to First Use of Rescue Medication	Population mITT

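### SAP 6.2 lets AEs related to medical history be captured as history without excluding post-dose worsening, so on one reading true TEAEs could leave the TEAE tables that SAP 9.2 defines

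*SAP*

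**What the plan says.** SAP 6.2 (Medical History) has a two-part rule. The first part takes "AEs that occur prior to treatment"; the second takes those "or that are related to a medical history event will be captured as medical history prior to database lock". The section gives no criterion for when an event is related to history, and mentions neither onset time nor worsening. On display it says: "Medical histories will also be presented in a by-subject listing using the coded and verbatim history terms". History is also tabulated in SAP Table 14.1.3, "Summary of Medical History".

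SAP 9.2 states: "Treatment-emergent AEs are defined as AEs that start or worsen in severity after the first exposure to study medication through the Day 7 visit". It makes no exception for events linked to medical history. All recorded AEs are to be listed, but only TEAEs are summarized. The columns and counts of the overall table are specified thus: "giving for each treatment group, all DFN-15 groups combined and overall of both the number of events and the number of subjects with TEAEs".

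The protocol agrees with SAP 9.2. Protocol 7.5 defines a TEAE as an AE that begins, or worsens in severity, after dosing. Protocol 7.1 gives exacerbation of a pre-existing condition, in frequency or intensity, as an example of an AE. It excludes expected fluctuation of a pre-existing condition only where there is no worsening.

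**The concern.** A known condition that gets worse after dosing fits both rules. It is related to a medical history event, so SAP 6.2 captures it as history; it worsened after first exposure, so SAP 9.2 counts it as a TEAE. If the first rule takes the event out of the AE data before lock, the second never sees it, and the TEAE tables undercount.

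Protocol section 2 makes tolerability and safety the secondary objective, and incidence of AEs and SAEs is the first safety endpoint in Protocol 8.2.3. The ambiguity bites during data review before lock, when someone decides which entries to reclassify. It does not bite in programming, because under SAP 3.0 the finished SDTM and ADaM "data sets will be taken as input to the SAS programs that generate the report-ready tables, figures and listings". A program applying SAP 9.2 correctly could not restore an event already removed from the AE data.

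**Working it through.** The plan gives no figure to reproduce. The check is mainly a comparison of passages, with simple arithmetic for scale.

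**Step 1: what the second part of SAP 6.2 adds.** The first part already takes every AE before treatment. If the second part is to add anything, it must reach AEs at or after dosing. Nothing in the sentence confines it to conditions that stayed the same.

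**Step 2: the rules applied to three kinds of event.**

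| Event | SAP 6.2, read literally | SAP 9.2 | Protocol 7.1 / 7.5 |
|---|---|---|---|
| AE before dosing, no later worsening | History (first part) | Not a TEAE | Not a TEAE |
| Entry made after dosing that only restates a known, unworsened condition | History (second part) | Not a TEAE, since it neither starts nor worsens after exposure | Not an AE |
| Known condition that worsens in severity after dosing | History (second part) | TEAE | AE and TEAE |

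The rules clash only in the last row.

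**Step 3: is there a tie-break?** SAP 3.0 says that "the rules set forth in the specific section take precedence over the general policies". Sections 6.2 and 9.2 are both specific sections, so this does not rank one above the other. Protocol 8.3.1 lets the SAP prevail over the protocol where they differ, so the protocol definitions can guide the reading of SAP 6.2 but cannot be relied on to override it.

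**Step 4: does capture as history mean removal from the AE data?** SAP 6.2 does not say so. Two readings are open:
- *Moved.* The event leaves the AE data and shows only in Table 14.1.3 and Listing 16.2.3. It misses the TEAE tables.
- *Added.* The event is also recorded as history but stays in the AE data. SAP 9.2 then counts it and there is no conflict. The SAP 9.2 contrast between listed and summarized AEs, the column of Table 2 for AEs dated before treatment, and Listing 16.2.11.1 of all AEs all fit this reading.

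**Step 5: scale per event, on the moved reading.** Inputs: 120 subjects randomized 1:1:1:1 (SAP 2.2, 2.6), assuming all are dosed.
- Per arm: 120/4 = 30. DFN-15 combined: 3 × 30 = 90. Overall: 120.
- One subject whose sole TEAE is moved: 1/30 = 3.3 points in the arm and 1/120 = 0.8 points overall. If that subject is on DFN-15, the combined column also falls by 1/90 = 1.1 points; if on placebo, by 0.
- A subject who has another TEAE: 0 points in overall subject incidence, but the event count falls by 1, and the SOC/PT row of the moved event can lose that subject.

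These are effects per subject. The documents give no count of such events, and none is assumed.

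**The case against.** The best case for the plan is that SAP 6.2 was meant narrowly. It sits under baseline characteristics and speaks of history collected at screening. Two parts joined by an or may overlap. Even if the second part works only after dosing, it has ordinary targets that involve no worsening: entries that restate a known condition, or entries with no start date, which SAP Table 2 assigns to the date of first treatment. Read consistently with SAP 9.2 and Protocol 7.1 and 7.5, SAP 6.2 creates no discrepancy at all, so invoking the SAP's priority over the protocol presupposes the broad reading. Much of this stands: the narrow intent is likely. But SAP 6.2 does not state it, and someone following the sentence literally could reclassify a true TEAE.

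The objection on size also stands. Subjects are generally healthy, receive one dose and are followed to Day 4 to 10. Safety is summarized without testing, and 1/30 is simply the weight of one subject in any arm-level table.

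A reader might infer more: that SAP 6.2 strips these events from the AE record so that they appear only as history, that the tables would favour DFN-15, or that events could be recoded with knowledge of treatment. The documents support none of these. SAP 6.2 never says only, and several SAP passages fit events staying in the AE data. The rule applies alike to all arms, and no difference between arms is shown. Protocol 5.8 blinds site assessors and sponsor personnel, and reclassification precedes database lock.

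**Conclusion.** The point holds as a minor wording defect. SAP 6.2 states a reclassification rule without the no-worsening limit of Protocol 7.1, and nothing in the SAP ranks it against SAP 9.2. Whether TEAEs would actually be lost depends on two things the documents leave open: that capture as history means removal from the AE data, and that the second part is applied to worsened conditions. If both hold, each subject whose sole TEAE is moved costs 3.3 points in an arm of 30 and 0.8 points overall, assuming all 120 are dosed. The number of such subjects is unknown and probably small. Even on that reading the events remain visible as medical history. SAE reporting to the sponsor and the efficacy analyses are unaffected.

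**What to change.** In SAP 6.2, limit the rule to:
- events with onset before first dose that do not worsen in severity after dosing; and
- AE-log entries that only restate a pre-existing condition that did not worsen, which are not AEs under Protocol 7.1.

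Then state that any AE that starts or worsens in severity after first exposure stays in the AE data and is summarized as a TEAE under SAP 9.2.

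SAP 9.2 and Protocol 7.5 speak of severity only, whereas Protocol 7.1 also counts increased frequency of a pre-existing condition as an AE. If increased frequency is also to make an event treatment-emergent, the SAP 9.2 definition has to be amended to say so; a change to SAP 6.2 alone would not do it.

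The cost is two or three sentences, settled before database lock, with no new data or analysis. The downside is that reported TEAE incidence may rise slightly.
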